### 5.5.2 Visit 2 (week 1) (part I)

- 1. Question the subject about occurrence of adverse events (AEs) and assess local tolerability (see section 7.2). Record occurrence of any events and/or any changes in events that were ongoing at the previous clinical trial visit. Document all changes in the eCRF.
- 2. Enquire whether any concomitant therapies have been added, stopped, or changed since the subject's last visit. Document all changes in the eCRF.
- 3. Count atrophic acne scars of each half-face (see section 7.1.1).
- 4. Perform an Investigator's Scar Global Assessment (SGA) of each half-face (see section 7.1.2).
- 5. Count inflammatory, non-inflammatory acne lesions and nodules of each half-face (see section 7.1.4).
- 6. Perform an Investigator's Global Assessment (IGA) of each half-face (see section 7.1.5).
- 7. The product dispenser will:

- a. Assess subject's compliance based on the subject's compliance report available on Triacys website and discussion with the subject and report in the eCRF any missing or incomplete product application record as indicated in the product dispensation log.
- b. Download data from the "Study Companion" tablet.
- c. Emphasize again the importance of complying with the given instructions and treatments; instruct the subject to bring back the dispensed investigational products together with the "study companion" tablet at the next visit.
- d. For all female subjects, emphasize the guidelines about contraception and risks in case of pregnancy.
- 8. Schedule the next follow up visit in three weeks  $\pm$  3 days

# 5.5.3 Visit 3 (week 4), 4 (week 8), 6 (week 16) and 7 (week 20) (part I)

- 1. Question the subject about occurrence of adverse events (AEs) and assess local tolerability (see section 7.2). Record occurrence of any events and/or any changes in events that were ongoing at the previous clinical trial visit. Document all changes in the eCRF.
- 2. Enquire whether any concomitant therapies have been added, stopped, or changed since the subject's last visit. Document all changes in the eCRF.
- 3. Conduct a urine pregnancy test (UPT) for female subjects of childbearing potential.
- 4. Count atrophic acne scars of each half-face (see section 7.1.1).
- 5. Perform an Investigator's Scar Global Assessment (SGA) of each half-face (see section 7.1.2).
- 6. Count inflammatory, non-inflammatory acne lesions and nodules of each half-face (see section 7.1.4).
- 7. Perform an Investigator's Global Assessment (IGA) of each half-face (see section 7.1.5).
- 8. The product dispenser will:
  - a. Check the returned investigational products.
  - b. Assess subject's compliance based on the subject's compliance report available on Triacys website and discussion with the subject and report in the eCRF any missing or incomplete product application record as indicated in the product dispensation log.
  - c. Download data from the "Study Companion" tablet.
  - d. Dispense from the subject kit the applicable visit treatment box.
  - e. Affix the tear-off portion of the labels on the product dispensation log.
  - f. Dispense to the subject the associated non-investigational clinical trial products with explanations how and when to use them *(only applicable at visit 4 (week 8) and visit 6 (week 16)).*

- g. Remind to the subject the importance of complying with the given instructions and treatments and to bring back the investigational products together with the "Study Companion" tablet at the next visit.
- h. For all female subjects, emphasize the guidelines about contraception and risks in case of pregnancy.
- 9. Schedule the next follow up visit in:
  - If at visit 3 (week 4): in four weeks  $\pm$  3 days
  - If at visit 4 (week 8), visit 6 (week 16) or visit 7 (week 20): in four weeks  $\pm$  1 week

# 5.5.4 Visit 5 (week 12) (part I)

- 1. Question the subject about occurrence of adverse events (AEs) and assess local tolerability (see section 7.2). Record occurrence of any events and/or any changes in events that were ongoing at the previous clinical trial visit. Document all changes in the eCRF.
- 2. Enquire whether any concomitant therapies have been added, stopped, or changed since the subject's last visit. Document all changes in the eCRF.
- 3. Conduct a urine pregnancy test (UPT) for female subjects of childbearing potential.
- 4. Count atrophic acne scars of each half-face (see section 7.1.1).
- 5. Perform an Investigator's Scar Global Assessment (SGA) of each half-face (see section 7.1.2).
- 6. Assess investigator's preference in terms of overall scar severity (see section 7.1.3);
- 7. Count inflammatory, non-inflammatory acne lesions and nodules of each half-face (see section 7.1.4).
- 8. Perform an Investigator's Global Assessment (IGA) of each half-face (see section 7.1.5).
- 9. Assess the skin roughness score of each half-face (see section 7.1.6).
- 10. Assess the skin texture change score for each half-face (see section 7.1.7).
- 11. For selected sites only (and only if subject and parent/guardian accept through the approved ICF, if applicable), take photographs of the face according to the provided procedure.
- 12. Provide guidance on the SCARS questionnaire and ask the subject to fill it out for each half-face (see Appendix 1).
- 13. The product dispenser will:
  - a. Check the returned investigational products.
  - b. Assess subject's compliance based on the subject's compliance report available on Triacys website and discussion with the subject and report in the eCRF any missing or incomplete product application record as indicated in the product dispensation log.
  - c. Download data from the "Study Companion" tablet.
  - d. Dispense from the subject kit the week 12 visit treatment box.

- e. Affix the tear-off portion of the labels on the product dispensation log.
- f. Remind to the subject the importance of complying with the given instructions and treatments and to bring back the investigational products together with the "Study Companion" tablet at the next visit.
- g. For all female subjects, emphasize the guidelines about contraception and risks in case of pregnancy.
- 14. Schedule the next follow up visit in four weeks  $\pm 1$  week

# 5.5.5 Visit 8 (week 24) (end of part I, beginning of part II)

- 1. Question the subject about occurrence of adverse events (AEs) and assess local tolerability (see section 7.2). Record occurrence of any events and/or any changes in events that were ongoing at the previous clinical trial visit. Document all changes in the eCRF.
- 2. Enquire whether any concomitant therapies have been added, stopped, or changed since the subject's last visit. Document all changes in the eCRF.
- 3. Conduct a urine pregnancy test (UPT) for female subjects of childbearing potential.
- 4. Count atrophic acne scars of each half-face (see section 7.1.1).
- 5. Perform an Investigator's Scar Global Assessment (SGA) of each half-face (see section 7.1.2).
- 6. Assess the Investigator's preference on overall scar severity (see section 7.1.3).
- 7. Count inflammatory, non-inflammatory acne lesions and nodules of each half-face (see section 7.1.4).
- 8. Perform an Investigator's Global Assessment (IGA) of each half-face (see section 7.1.5).
- 9. Assess the skin roughness score of each half-face (see section 7.1.6).
- 10. Assess the skin texture change score for each half-face (see section 7.1.7).
- 11. For selected sites only (and only if subject and parent/guardian accept through the approved Informed Consent Form, if applicable), take photographs of the face according to provided procedure.
- 12. For selected sites only, make skin replica for each half-face (if consent given) (see section 7.1.8).
- 13. Provide guidance on the SCARS questionnaire and ask the subject to fill it out for each half-face (see Appendix 1).
- 14. Provide guidance on the satisfaction questionnaire part I and ask the subject to fill it out (see Appendix 2).
- 15. For subjects considered to enter part II of the clinical trial, explain the nature and the constraints of the part II of the clinical trial to the subjects and to his/her parent(s) or guardian if the subject is under the age of 18.

- 16. If a female subject of childbearing potential agrees to participate in part II of the clinical trial, make sure she agrees to continue using the requiring method(s) of contraception.
- 17. Ensure the subject (and parent/guardian for subjects under the age of 18) has read, understood, dated and signed the approved ICF for part II.
- 18. Give a dated and signed copy of the ICF for part II to each subject and parent/guardian if applicable.
- 19. Fill in the prescription form.
- 20. The product dispenser will:

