#### 4.3.4 Authorized therapies during the clinical trial

Unless listed under the exclusion criteria (section 4.2.2 items 9 and 10) or in prohibited therapies (section 4.3.5), all therapies are authorized.

Subject may use moisturizer as required for the symptomatic relief of skin dryness or irritation (use of moisturizer other than the one provided for this clinical trial will be captured into the eCRF as concomitant therapy).

Oral vitamin A supplement (up to the recommended daily allowance) and plain penicillin are acceptable.

Systemic anti-inflammatory medication up to 21 days of treatment in total is also acceptable; however, it should be avoided for 1 week prior to the week 24 visit (primary endpoint assessment).

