### 5.5 CLINICAL TRIAL VISIT DESCRIPTION AND PROCEDURES

# 5.5.1 Visit 1 (baseline) (part I)

- 1. Explain the nature and the constraints of the clinical trial to the subject and to his/her parent(s) or guardian if the subject is under the age of 18.
- 2. If a female subject of childbearing potential agrees to participate to the clinical trial, make sure she is using the requiring method(s) of contraception.
- 3. Ensure the subject (and parent/guardian for subjects under the age of 18) has read, understood, dated and signed the approved Informed Consent Form (ICF).
- 4. Give a dated and signed copy of the ICF to each subject and parent/guardian if applicable.
- 5. Log into the electronic Case Report Form (eCRF) to get a Subject Identification Number (SIN)
- 6. Question the subject about demography (birthdate, race, skin phototype, gender), relevant medical history, prior therapies (stopped within 6 months of the baseline visit and that may have an impact on the inclusion/exclusion criteria) and concomitant therapies.
- 7. Inform subject about authorized and prohibited concomitant therapies.
- 8. Check inclusion/exclusion criteria (see sections 4.2.1 and 4.2.2).
- 9. Conduct a urine pregnancy test (UPT) for female subjects of childbearing potential.
- 10. Count atrophic acne scars of each half-face (see section 7.1.1).
- 11. Perform an Investigator's Scar Global Assessment (SGA) of each half-face (see section 7.1.2).
- 12. Count inflammatory, non-inflammatory acne lesions and nodules of each half-face (see section 7.1.4).
- 13. Perform an Investigator's Global Assessment (IGA) of each half-face (see section 7.1.5).
- 14. Assess the skin roughness score of each half-face (see section 7.1.6).
- 15. Perform the baseline Local Tolerability Assessment (erythema, dryness, scaling, stinging/burning; see Section 7.2.1). Note: Stinging/burning at the baseline visit should be assessed as None (0).
- 16. For selected sites only (and only if subject and parent/guardian accept through the approved ICF, if applicable), take photographs of the face according to the provided procedure.
- 17. For selected sites only, make skin replica for each half-face (if consent given) (see section 7.1.8).
- 18. Provide guidance on the SCARS questionnaire and ask the subject to fill it out for each half-face (see Appendix 1).

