### 6.3.2 Dispensing

All investigational and non-investigational products will be provided only to subjects enrolled into the clinical trial, at no cost and in accordance with the conditions specified in the protocol.

Dispensation will be appropriately documented on the appropriate product dispensation log by the product dispenser at each visit.

It is important that no subject runs out of clinical trial supplies between visits.

The product dispenser will follow the accurate prescription according to the allocated kit (applicable during part I only).

During part I, each subject will receive a new visit box containing one pump of each investigational product at baseline and each post-baseline visit except at week 1 and week 24.

During part II, each subject will receive 3 bottles of Tactupump™ Forte / CD0271 0.3%/CD1579 2.5% gel at the week 24 and week 36 visits.

During part I, all efforts will be taken to keep the evaluator (investigator or designee) blinded by restricting his/her contact with the investigational products.

GALDERMA RESEARCH & DEVELOPMENT Protocol N° RD.03.SPR.105061 Page 50 of 99 CONFIDENTIAL

The product dispenser must be different from the clinical trial efficacy and safety evaluator in order to maintain the blind during part I (see section 6.5).

During part I, treatment kits will be dispensed in ascending sequential order according to the chronological order of enrolment of subjects into the clinical trial.

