## 7.1 EFFICACY ASSESSMENTS

Clinical evaluations should be performed by the same evaluator (investigator or designee) throughout the clinical trial.

If it is not possible to use the same evaluator to follow a subject, then evaluations should overlap for at least one visit in order to examine the subject together and discuss findings and this should be documented in the source documents. At least for the baseline assessments and the final assessments of part I (week 24/early termination), the evaluator should be the same person.

The evaluated areas must be examined under the same conditions of light exposure at each visit (same angle to avoid shadow and same light source, i.e. artificial or daylight).

Both during part I and part II, the zone in the middle of the face (approximately 2 cm large and the nose) will be excluded for the clinical efficacy evaluations because subjects may apply a mix of both investigational products (active and vehicle) on this zone. See figure below.

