### 7.2.1 Local tolerability assessment

Signs and symptoms of local cutaneous irritation (erythema, scaling, dryness and/or stinging/burning) are possible during treatment with Adapalene 0.3% - BPO 2.5%.

The investigator will evaluate erythema, scaling, dryness and/or stinging/burning at each trial visit. The investigator will record stinging/burning after discussion with the subject regarding the previous application days. The investigator will ask an open-ended question, taking care not to influence the subject's answer, such as: "Have you experienced any sensations immediately following products application (within 5 minutes)?"

GALDERMA RESEARCH & DEVELOPMENT Protocol N° RD.03.SPR.105061 Page 59 of 99 CONFIDENTIAL

Erythema, scaling, dryness, and stinging/burning will be graded at baseline and each post-baseline visit as follows (to be done for each half-face):

• **Erythema**: abnormal redness of the skin

None 0: No erythema

Mild 1: Slight pinkness present

Moderate 2: Definite redness, easily recognized

Severe 3: Intense redness

• Scaling: abnormal shedding of the stratum corneum

None 0: No scaling

Mild 1: Barely perceptible shedding, noticeable only on light scratching or rubbing

Moderate 2: Obvious but not profuse shedding

Severe 3: Heavy scale production

• **Dryness**: brittle and/or tight sensation.

None 0: No dryness

Mild 1: Slight but definite roughness

Moderate 2: Moderate roughness Severe 3: Marked roughness

• Stinging/Burning: prickling pain sensation immediately after application (within 5 minutes).

None 0: No stinging/burning

Mild 1: Slight warm, tingling/stinging sensation; not really bothersome

Moderate 2: Definite warm, tingling/stinging sensation that is somewhat bothersome Severe 3: Hot, tingling/stinging sensation that has caused definite discomfort

Note: Stinging/Burning at the baseline visit should be assessed as none (0).

An Adverse Event will be recorded if the severity of the signs and symptoms is such that:

- The subject's participation in the trial is interrupted at his/her request or at the investigator's request after the week 4 visit
- The subject permanently discontinues the treatment at his/her request or at the investigator's request.
- The subject requires concomitant prescription or OTC therapy (other than moisturizers).

Note: Need for increased moisturizer use does NOT constitute an AE.

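### Minor, cheap improvement: at post-baseline part I visits the listed steps put adverse-event, per-side tolerability and concomitant-therapy questions before scar scoring, and no blinding measure sets the order

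*Protocol*

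**What the plan says.** The week 24 list (protocol 5.5.5) shows the pattern. Item 1 is "Question the subject about occurrence of adverse events (AEs) and assess local tolerability (see section 7.2"). Item 2 is "Enquire whether any concomitant therapies have been added, stopped, or changed". Item 3 is the pregnancy test. Item 4 is "Count atrophic acne scars of each half-face (see section 7.1.1"), followed by the SGA (item 5) and the investigator's preference (item 6). Weeks 4 to 20 (5.5.3, 5.5.4) also have the scar count at item 4. Week 1 (5.5.2) has no pregnancy test, so the count is item 3. Early termination uses the list of the next planned visit (5.5.8).

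Tolerability is graded for each half-face (7.2.1), and one component comes only from the subject: "The investigator will record stinging/burning after discussion with the subject regarding the previous application days". On who does what, 6.3.2 says "The product dispenser must be different from the clinical trial efficacy and safety evaluator in order to maintain the blind during part I", and 7.1 says "Clinical evaluations should be performed by the same evaluator (investigator or designee) throughout the clinical trial".

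Section 6.5.1 lists four blinding measures: identical packaging, a separate dispenser, an instruction not to discuss the products with the evaluator, and no access to the randomization list. None concerns the order of assessments.

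Baseline (5.5.1) is listed differently. Efficacy is scored at items 10 to 14, then item 15 is "Perform the baseline Local Tolerability Assessment (erythema, dryness, scaling, stinging/burning; see Section 7.2.1"), and the adverse-event question is item 19. Concomitant therapies are asked earlier, at item 6.

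**The concern.** Sections 2.3.2 and 6.4 expect irritation from the active gel. If a subject says that one side stings, the evaluator has a plausible pointer to the active side. The next evaluator tasks listed are a subjective scar count on each side, a global scar grade on each side and, at two visits, a direct left-right preference. Pairing within subject does not cancel a bias of this kind, because the cue itself differs between the sides.

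Visible signs cannot be hidden from someone examining the face. Stinging and burning are different: the evaluator learns of them only by asking, so at a given visit this cue can be avoided by scoring first. The required question in 7.2.1 about sensations after application also sits awkwardly with the instruction in 6.5.1 not to discuss the products. Scoring first limits what that conversation can influence at that visit.

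**Working it through.** **Position of the scores in the lists.** Weeks 1, 4, 8, 16 and 20 have 4 evaluator efficacy scores each (scar count, SGA, lesion count, IGA). Weeks 12 and 24 have 7 each (adding preference, roughness, texture). Per completing subject this is 5 × 4 + 2 × 7 = 34. Baseline has 5 (scar count, SGA, lesion count, IGA, roughness). The comparison has to be made separately for each kind of question:

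| Scores listed after | Post-baseline part I | Baseline |
|---|---|---|
| Tolerability and adverse-event questions | 34 of 34 | 0 of 5 |
| Concomitant-therapy question | 34 of 34 | 5 of 5 |

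Baseline is thus a precedent for scoring before tolerability and adverse events, but not for scoring before the therapy question. These are list positions; they do not measure bias.

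**What reordering withholds.** Tolerability is graded per side at every visit, and 7.1 asks for one evaluator throughout. If that person also takes the tolerability reports, the week 1 grades are known before the week 4 scar count, whatever the order at week 4. Scoring first therefore withholds all earlier per-side reports only at week 1. At week 4, at later visits and at early termination it withholds only what is new since the last visit.

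**Which tests are touched early.** Section 6.4 places irritation mostly in the first four weeks. SAP 6.3.2 tests the secondary variables at every post-baseline time. At weeks 1 and 4 this gives 3 scar endpoints (count, percent change, SGA) × 2 visits = 6 tests. The 3 at week 1 would be fully protected from subject-reported cues and the 3 at week 4 only partly. None decides the trial: success is p < 0.05 at week 24 (protocol 9.1.4, SAP 6.3.1).

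**Scale for the primary endpoint.** From 9.2.1, SD 4.8 and mean difference 2. The planned size reproduces: (4.8 × (1.960 + 0.842) / 2)² = 45.2 by the normal formula, 48 by the paired t-test, and 48 × π/3 = 50.3 after allowing for Wilcoxon efficiency, against the stated 50. With 60 in the ITT analysis, SE = 4.8/√60 = 0.62.

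One route to week 24 is an early-termination count carried forward by LOCF (9.1.2.4, SAP 5.4). If k subjects have a count shifted by d scars, the mean difference moves by k × d / 60. Both inputs are assumptions; the documents give neither. With d = 1:
- k = 3: 3/60 = 0.05 scar, or 0.05/0.62 = 0.08 SE
- k = 12: 12/60 = 0.20 scar, or 0.20/0.62 = 0.32 SE

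The shift scales in proportion to d. Twelve is 20% of 60, the whole exclusion allowance in 9.2.2, which also covers major deviations and losses to follow-up, so it is an upper bound for k. Reordering could prevent only the part of the shift that comes from reports new at the termination visit.

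**The case against.** The strongest reply is that the protocol requires no order. The steps are numbered, but nothing makes the sequence binding, and the flow chart (5.4) lists the scar count above tolerability. Section 10.1 mentions a trial reference manual and specific training on scar assessment. Neither is among the documents, so sites may have had an order. This stands: the gap is a silence in the protocol, not a stated error.

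It also stands that baseline is before treatment, so its order was not necessarily chosen to protect the blind. The therapy question is a weaker cue. Section 4.3.4 says only that "use of moisturizer other than the one provided for this clinical trial will be captured into the eCRF as concomitant therapy", and no passage says that therapies are recorded by side. There are partial safeguards: subjects are told not to discuss the products, and 6.4 suspends both half-faces together, so a suspension does not by itself identify a side. Section 6.3.2 suggests one person for efficacy and safety but does not require it; 7.1 allows a designee to score efficacy, while 7.2.1 gives tolerability to the investigator.

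A reader might infer that the blind is broken, or that the primary test has an inflated false-positive rate. The documents do not support this. Simulation with no true effect, n = 60 and SD 4.8 gives about 34% rejection if every trial has a mean bias of one scar toward the active side, but nothing in the documents links assessment order to a bias of that size. A reader might also infer equal protection at weeks 1 and 4; the evaluator's knowledge of earlier grades rules that out.

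None of this shows that asking first is harmless, or that scoring first has a material drawback.

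**Conclusion.** The point holds as a minor improvement. An avoidable same-visit cue to the active side is listed ahead of subjective side-to-side scoring, and the blinding section does not address it. This rests on two assumptions: that sites follow the listed order, and that one person both takes the tolerability report and scores the scars. The text permits both and requires neither.

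The gain is partial. Visible erythema or scaling, one-sided clearing of lesions (expected from 2.1 and 3.2) and memory of earlier visits would remain, and are probably the larger cues by week 24. At a termination prompted by irritation, the investigator may already know of it. The size of any order effect cannot be obtained from the documents, and the effect on the week 24 primary result is probably small.

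**What to change.** State in 5.5.2 to 5.5.5, and in 5.5.8 for part I, that every evaluator efficacy score due at the visit (scar count, SGA, preference, lesion count, IGA, roughness, texture) is completed and recorded before the planned adverse-event, tolerability and concomitant-therapy questions. Arrange the source worksheets in the same order. If the trial reference manual already sets an order, align it. Part II is open-label and needs no change.

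The cost is one sentence per visit section, reordered worksheets and a short protocol amendment, which may need IRB/EC approval under 11.1 in Canada and France. No staff or procedures are added, no safety assessment is removed or altered, and tolerability stays with the investigator as 7.2.1 assigns it. One small point is my inference: sizing scars with punch tools first might slightly affect erythema grading, but baseline already uses that order.
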